9.2. Definition of End of Trial

The end of trial is the date of the last clinic visit, at 12 months post-operatively, of the last recruited participant.

10. SAFETY REPORTING

Surgery

All participants will be recruited from a population that are on waiting lists for total hip arthroplasty surgery at one of the participating centres. All procedures will be carried out in accordance with existing practice and therefore participation in the study will not confer any increased risk. Surgical risks are minor and rare but include infection, thromboembolism, persistent pain, bleeding, damage to nerves of blood vessels, stiffness, injuries caused by traction and failure of procedure.

The insertion of the pelvic screw into the pelvis is the additional step in the intervention arm that carries risk. Risks from this part of the procedure would be similar to those of the control arm surgery itself in terms of pain, bleeding, infection, damage to nerves or blood vessels, or failure of procedure. The risk of infection in both procedures is minimised by the use of prophylactic antibiotics. Complications from the surgery will be monitored as per each NHS trust protocol for routine postoperative care. This involves regular monitoring by nursing staff and doctors for evidence of postoperative complications whilst the participant is an inpatient, and at every follow up visit when the patient is an outpatient. Wound sites will be checked for evidence of infection, collections, or failure to heal, observations will be monitored for signs of infection or complication, and blood tests will be monitored for evidence of bleeding, infection, or electrolyte imbalance. The patient will only be discharged from in-patient care once both medical and physiotherapy teams agree that the patient is safe for discharge as per standard postoperative protocol.

10.1. Definition of Serious Adverse Events

A serious adverse event is any untoward medical occurrence that:

- results in death
- is life-threatening
- requires inpatient hospitalisation or prolongation of existing hospitalisation
- results in persistent or significant disability/incapacity
- consists of a congenital anomaly or birth defect.

Other 'important medical events' may also be considered serious if they jeopardise the participant or require an intervention to prevent one of the above consequences.

NOTE: The term "life-threatening" in the definition of "serious" refers to an event in which the participant was at risk of death at the time of the event; it does not refer to an event which hypothetically might have caused death if it were more severe.

10.2. Reporting Procedures for Serious Adverse Events

A serious adverse event (SAE) occurring to a participant should be reported to the REC that gave a favourable opinion of the study where in the opinion of the Chief Investigator the event was 'related' (resulted from administration of any of the research procedures) and 'unexpected' in relation to those procedures. Reports of related and unexpected SAEs should be submitted within 15 working days of the Chief Investigator becoming aware of the event, using the HRA [report of serious adverse event](#) form (see HRA website). Any adverse event considered to be related to any devices supplied by Corin shall be submitted to Corin via <https://vigilance.coringroup.com/vigilance-form/>.

11. STATISTICS

11.1. The Number of Participants

The study's aim is to determine whether the Corin OPS system reduces dislocation rate, compared to standard surgical technique and templating. A literature review found that the dislocation rate after THA was 5.0%^{11,17,18}. A clinically significant difference of interest of 4.5% will be used in this study, meaning the required dislocation rate in the OPS group is <0.5%. We performed a power calculation, with α significance of 0.05 and power of 0.8, which gave a required sample size of 414 participants. Accounting for a dropout rate of 10%, this gives a total required sample size of 460, with 230 participants in each arm.

The first 100 participants recruited will be entered into an internal pilot study. The internal pilot study will study the rate of recruitment of participants and analyse whether completion of recruitment of all patients is feasible within our time limits. If the internal pilot study shows that completing the study is unfeasible, then the full trial will be terminated. The internal pilot study will allow calculation of a provisional dislocation rate (the primary outcome) in the control arm of the study. The rationale for this is that the control arm participants may have a different dislocation rate to that found in our literature review. Using the dislocation rate in the internal pilot study and the minimum clinically significant difference of interest, we will re-calculate the sample size required to fully power the full study. We expect, therefore, that the full study sample size may change by 5% either way from our projected sample size of 476 participants. However, if the size of the cohort increases by more than 5% (to above 500) we may need to re-approach the funder to enable us to recruit additional participants.

The subgroup of 50 participants receiving gait analysis pre-operatively and at 12-month post-operatively will include 25 participants from each study arm. The sample size of 50 is of sufficient size to give detailed information. Analysis on a larger group is not possible due to gait laboratory capacity constraints.

The subgroup of participants receiving a 12-month post-operative CT scan will include 50 participants from the OPS arm. The position of the implant compared to the planned position will be analysed. The sample size of 50 is of sufficient size to give detailed information. Analysis on a larger subgroup is not possible due to financial constraints.

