2. SYNOPSIS

Trial Title	Does the Corin Optimised Positioning System improve clinical outcome in total hip arthroplasty? A multi-centre, two-arm randomised controlled trial	
Internal ref. no. (or short title)	The HAPI Trial	
Trial Design	Single-blinded randomised controlled trial comparing best practice total hip arthroplasty (THA) surgical technique and templating with the best practice THA surgical technique plus Corin Optimised Positioning System (OPS) to guide templating. We will perform an internal pilot after 100 participants have been recruited. If analysis shows the trial is feasible, we will then progress onto the full study.	
Trial Participants	Male and female adults between 18 and 85 years of age, with a dysfunctional hip caused by osteoarthritis (OA), post traumatic OA, inflammatory arthropathy, avascular necrosis and congenital/developmental problems, randomly selected from the THA waiting list at each participating centre.	
Planned Sample Size	460 participants. 230 patients will receive best practice THA with conventional templating; the other 230 will receive best practice THA with Corin OPS to guide templating. Patients who drop out will not be replaced. The first 100 patients will constitute an internal pilot: results of the internal pilot will be used to repower the study. We anticipate the projected sample size of 460 may change by 5% either way.	
Treatment duration	2 years	
Follow up duration	1 year	
Planned Trial Period	3 years	
	Objectives	Outcome Measures
Primary	To compare the efficacy of the Corin OPS system to guide templating in THA with standard templating in THA in reducing dislocation	Dislocation rate and re-operation for dislocation rate
Secondary	1. To determine whether the Corin OPS System improves Harris hip score, patient reported outcome measures (PROMs), reduces hospital stay and normalises gait more effectively than conventional surgery	1. PROMs: 
• Oxford hip score (OHS)• iHOT33• HAGOS• Pain detect• EQ5D• UCLA score

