6. TRIAL DESIGN

This will be a multi-centre, two-arm, single blind (participant blind), randomised controlled group superiority study. It will take place in the NHS hospital setting. Stratification will be performed for age and sex by means of a minimisation technique during randomisation for each subject entering the trial. There will be no limit on the number of sites and no limit on the number of recruits per site. The study site shall maintain a list of the participating sites and investigators separately to the protocol.

Arm 1

Best practice total hip arthroplasty with conventional templating

Arm 2

10/11/17

Protocol 1.2

Page 9 of 28

Does the Corin Optimised Positioning System improve clinical outcome in total hip replacement?

Chief Investigator: [name]

IRAS Project Number: 216084

Rec Reference Number: 17/SC/0506

Best practice total hip arthroplasty with Corin Optimised Positioning System to guide templating

In the study 230 participants will receive best practice THA with conventional templating; the other 230 will receive best practice THA with Corin OPS to guide templating. Any participant that withdraws from the study will not be replaced.

Initially we will perform an internal pilot study of 100 participants, with 50 participants in each arm. This will enable us to check feasibility of recruitment and to check our power calculation is correct. We anticipate recruitment to the pilot study will take six months, with an average of four participants recruited per week. Together the five centres currently recruited performed 3419 primary total hip replacements in 2015, an average of 66 per week⁸. Since participants in the two arms receive the same procedure, with the difference being in the technique used, with clear explanation of the trial to potential participants, we anticipate that approximately 50% of eligible patients that are approached will consent to take part in the trial. With this knowledge, we believe recruitment of initially four (rising to six) participants per week will be attainable. If the internal pilot study shows that completing the study is unfeasible, then the trial will be terminated following mutual agreement from both the Chief Investigator and the funder (Corin Limited). We anticipate recruitment to the full trial will take two years.

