8.6. Summary of Visits

Routine clinical practice will take priority and the study timetable has been drawn up to allow the study procedures to fall within current surgical waiting times. Taking part in the study, therefore, will not delay or expedite treatment. Below is a summary of what will take place at each visit:

Visit 1: Consent visit

- Scheduled within 4-6 weeks of when potential participants are initially approached
- Consent form discussed and signed
- Following this visit, participants will be randomised into one of the two study arms
- If patients decline entry into the study, they will be offered entry into the 3rd observational arm of the study

Visit 2: Baseline assessment visit

- Scheduled for soon after consent visit
- Baseline assessments (detailed in section 8.5) completed

Visit 3: Gait Analysis Visit (subset of patients only)

- Scheduled for same day as or soon after baseline assessment visit (because scheduling CT scan and gait analysis on the same day may not be possible)

Visit 4: Study intervention

- Scheduled for 6-8 weeks after the baseline assessment (Thus patients will have a wait for surgery of approximately 3 months after entry into the study, which is in line with the current surgery waiting time in the participating centres.) Participants will undergo THA surgery in accordance with their randomisation allocation.
- Operative details to be collected:

- Date of surgery
- Randomisation group
- Name of consultant in charge of care
- Grade of lead surgeon
- Grade of assistant surgeons
- Operative side
- Duration of surgery
- Estimated blood loss
- Surgical approach
- ASA grade
- Use of systemic prophylactic therapy (antibacterial and anticoagulant)
- Anaesthesia type
- Acetabular and femoral bone quality
- Whether there was an attempt to correct leg length (if so, what amount attempted and achieved)
- Occurrence of per-operative complications
- Ease of reduction
- Acetabular grafting performed
- Femoral grafting performed
- Details of hip prosthetic components used – including information from device labels
- Other comments on operation

Visit 5: 3-month post-operative visit

- Completion of PROM questionnaires
- Clinical assessment (to include full examination of hip joint and assessment of leg length discrepancy)
- Recording of dislocations, further surgeries or adverse events
- Recording of details of any other healthcare usage by the participants (for cost analysis)

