11.3. The Level of Statistical Significance

All hypothesis testing will be performed at the two-sided 5% level of significance.

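### The internal pilot re-powers the trial from a control dislocation rate with no set follow-up or denominator; read at the 100th recruit, it would probably be well below the 12-month rate

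*Combined protocol and SAP*

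**What the plan says.** The synopsis (section 2) sets the trigger: "We will perform an internal pilot after 100 participants have been recruited". Section 6 gives its timing: "We anticipate recruitment to the pilot study will take six months, with an average of four participants recruited per week", with 50 participants per arm.

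Section 11.1 gives the pilot two tasks. One is to judge whether recruitment is feasible. The other concerns the primary outcome: "The internal pilot study will allow calculation of a provisional dislocation rate (the primary outcome) in the control arm of the study". This rate, together with the difference of interest, is then used to re-calculate the number of participants. An increase of more than 5% may mean going back to the funder.

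The outcome follows surgery. Section 5 assesses dislocation at 3, 6 and 12 months after the operation. On the wait for surgery, section 8.6 says: "Thus patients will have a wait for surgery of approximately 3 months after entry into the study". Section 6 agrees, with 15 months of participation in all. Section 8.6 also places surgery 6 to 8 weeks after a baseline visit that closely follows consent, so the 3 months could instead run from the first approach in clinic.

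Section 11.2 holds the analysis of the study until every participant has the 12-month assessment. It does not link that condition to the pilot rate.

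**The concern.** The trigger counts recruits, but the quantity wanted from the pilot can only be observed after surgery and follow-up. At the 100th recruit, many controls cannot yet have dislocated and the rest have been observed for a few weeks. A low rate at that point could reflect missing follow-up and still be read as a low true control rate.

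At stake is the size of the trial. The rate is the only new input to the recalculation, and an immature value makes that recalculation either impossible or misleading.

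**Working it through.** **1. The plan's own sample size.** Inputs from section 11.1: control rate ("A literature review found that the dislocation rate after THA was 5.0" per cent), difference ("A clinically significant difference of interest of 4.5% will be used in this study"), so 0.5% in the OPS arm, "with α significance of 0.05 and power of 0.8". Section 11.3 makes it two-sided: "All hypothesis testing will be performed at the two-sided 5% level of significance". Pooled-variance formula for two proportions, no continuity correction:

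n per arm = [1.960 × √(2 × 0.0275 × 0.9725) + 0.8416 × √(0.05 × 0.95 + 0.005 × 0.995)]² / 0.045² = (0.4533 + 0.1928)² / 0.002025 = 206.1, rounded up to 207.

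Total 414; 414 / 0.9 = 460. Both stated figures reproduce.

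**2. Status at the 100th recruit.** Four per week (section 6) gives 100 / 4 = 25 weeks. Assumptions: even accrual and a fixed wait of w weeks from consent to surgery. I use w = 13 for the stated 3 months, and w = 6 to 9 for the other reading of section 8.6 (baseline zero to one week after consent, then 6 to 8 weeks).

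- Operated = 4 × (25 − w)
- Reached 13 weeks after surgery = 4 × (25 − w − 13), or zero if negative
- Mean time since surgery = (25 − w) / 2

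| w (weeks) | Operated | Unoperated | Reached 13 weeks | Mean weeks since surgery |
|---|---|---|---|---|
| 13 | 48 | 52 | 0 | 6.0 |
| 9 | 64 | 36 | 12 | 8.0 |
| 6 | 76 | 24 | 24 | 9.5 |

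Placing the first entrant at week 0 adds one to each non-zero operated and 13-week count, giving 13 to 25 past 13 weeks on the shorter waits. If accrual takes 26 weeks with w = 13, the split is 50 operated and 50 not, still with none at 13 weeks.

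**3. Expected control dislocations.** Half of those operated are controls, and the true 12-month rate is taken as 5%. The documents do not say when dislocations occur, so three assumed timings span the range:

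- (a) Even over 52 weeks: controls operated × 0.05 × mean weeks / 52. For w = 13: 24 × 0.05 × 6 / 52 = 0.14.
- (b) All spread evenly over the first 13 weeks. For w = 13: 24 × 0.05 × 6 / 13 = 0.55. For w = 6: 12 controls past 13 weeks give 12 × 0.05 = 0.60, and 26 with a mean of 6.5 weeks give 26 × 0.05 × 0.5 = 0.65; total 1.25.
- (c) All at surgery: controls operated × 0.05. For w = 13: 24 × 0.05 = 1.2.

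| w | Events (a) / (b) / (c) | Rate over 50 randomised controls | Rate over operated controls |
|---|---|---|---|
| 13 | 0.14 / 0.55 / 1.2 | 0.3% / 1.1% / 2.4% | 0.6% / 2.3% / 5.0% |
| 9 | 0.25 / 0.95 / 1.6 | 0.5% / 1.9% / 3.2% | 0.8% / 3.0% / 5.0% |
| 6 | 0.35 / 1.25 / 1.9 | 0.7% / 2.5% / 3.8% | 0.9% / 3.3% / 5.0% |

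Full 12-month follow-up would give 50 × 0.05 = 2.5 events. With w = 13, the chance of no control event at all is 87% under (a) and 29% under (c).

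**4. Effect on the recalculation.** With the difference held at 4.5 points, a control rate below 4.5% implies a negative OPS rate, and no sample size exists. Over 50 randomised controls, 0, 1 or 2 events (0%, 2%, 4%) all fall there. Three events (6%) give 558, or 620 after dropout. So at least three events are needed for any answer, and 0.14 to 1.9 are expected.

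**5. When mature data arrive.** With w = 13:

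- All 100 past the 3-month visit: 25 + 13 + 13 = week 51. Recruited by then: 4 × 51 = 204 at four per week, or 100 + 6 × 26 = 256 at six per week after the pilot.
- All 100 past the 12-month visit: 25 + 13 + 52 = week 90. Recruited by then: 360 at four per week; 100 + 65 × 360 / 79 = 396 if the other 360 are spread to week 104; or all 460, reached at 25 + 360 / 6 = week 85, at six per week from the end of the pilot.

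**The case against.** The strongest reply is that no section says the rate is read on the day the 100th participant joins. Section 11.1 defines a cohort and gives no date; the six months in section 6 is the time to recruit that cohort. This is correct, so the defect is an unspecified cut-off. But recruitment is the only trigger stated, and reading the rate then is the natural way to follow the synopsis.

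Three stronger readings are tempting, and the documents do not support them.

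- **Half are always unoperated and none is ever at 3 months.** This holds on the 3-month wait, which the 15-month participation supports. It fails if surgery is 6 to 9 weeks after consent.
- **The rate is near zero by construction.** Over randomised controls it can reach 3.8%. Over operated controls it reaches 5.0% if every dislocation happens at surgery. A low rate is probable, but it depends on timing and denominator, and the plan gives neither.
- **Re-powering could never work on this timetable.** All 100 could complete the 3-month visit by about week 51, well inside the planned two years of recruitment. Even at week 90 some recruitment may remain, since section 6 gives no date for the rise to six per week.

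It can also be said that a rate below 4.5% makes the recalculation fail openly, and that 50 controls are few even with full follow-up: at a true 5%, the chance of two or fewer events is 54%. Both are true, and both concern the formula and precision. They do not repair the timing of the input.

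**Conclusion.** The point stands as a defect in the plan and should be corrected before the pilot decision. A recruitment-triggered pilot feeds a decision on trial size with a rate that has no defined follow-up or denominator. Read at the 100th recruit, 24 to 52 of 100 participants are unoperated and between none and about 25 have reached 3 months. The expected rate over 50 randomised controls is about 0.3% to 3.8% against a true 5%, so it is probably well below the 12-month rate and not a valid input for re-powering.

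This rests on even accrual of four per week, a fixed wait of 6 to 13 weeks from consent, a true 12-month control rate of 5%, and assumed dislocation timings from even over the year to all at surgery. In each scenario worked here, the expected rate over randomised controls is below both 5% and the 4.5% needed for the recalculation to exist. Only the limiting case of all events at surgery, counted among operated controls, recovers 5%.

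**What to change.** In sections 2, 6 and 11.1:

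1. Limit the month-6 decision to recruitment and consent feasibility, and state that the sample size is not re-calculated from the control rate at that point.
2. If a rate check is kept, tie it to follow-up, for example when all 100 pilot participants have completed the 3-month visit (about week 51 on the stated wait). Use a Kaplan-Meier estimate among operated controls. State that it informs the 12-month rate but does not estimate it, and that recruitment continues meanwhile.
3. In section 8.6, state the point from which the 3-month wait runs, so that the date of the check can be planned.

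The cost is protocol wording, with no extra participants or visits. The small downside is a later re-powering check, or none. A week-51 check would still be imprecise: mean follow-up would be 13 + 12.5 = 25.5 weeks, so expected control events run from 50 × 0.05 × 25.5 / 52 = 1.2 (risk even over the year) to 2.5 (all within 13 weeks).

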4. BACKGROUND AND RATIONALE

Osteoarthritis (OA) is the most common joint disease worldwide affecting an estimated 10% of males and 18% of females over 60 years of age¹. The resultant pain and loss of function can be debilitating and in developed countries represents a large socioeconomic burden, costing between 1% and 2.5% of gross domestic product, which currently stands at over £1.5 trillion². Total hip arthroplasty (THA) is an effective treatment for end-stage hip arthritis; however, demand for the procedure is growing rapidly, fuelled by an ageing population and the obesity epidemic³. In fact, rates of THA are predicted to rise 174% between 2005 and 2030⁴. The current commissioning environment in developed countries means that investment in iterative improvements of existing THA implant designs are unlikely to yield either significant benefits to patients or be supported by health funders. The two principle issues that concern surgeons and patients are the longevity of implants and the ability of new technologies to minimise complications such as dislocation and infection. The James-Lind Priorities Setting Partnership, an internationally recognised patient-driven organisation, has recently identified these pre-operative and intra-operative factors as targets for improving outcome following hip and knee replacement^{5,6}.

One of the largest costs to healthcare providers following THR is dislocation⁷. Although the dislocation rate reported in Joint Registries is between 1 and 3%^{8,9}, we know that this significantly underestimates the true problem, as the majority of dislocation events are managed with closed reduction and do not result in revision surgery¹⁰. It is estimated that dislocation is an order of magnitude more common than reported

in Registry data. Literature estimates indicate a true dislocation prevalence of 3 to 15%^{9,11,12}. The cost of dislocation is significant as the problem is often recurrent, resulting in multiple hospital admissions. The resulting average cost for each patient who suffers a THR dislocation is around £30,000⁷.

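### The pilot rule for recalculating N gives no answer when 0 to 2 of 50 controls dislocate (probability 0.54 at the planned 5%), cannot land within the expected ±5%, and is anchored on 476 although the plan derives 460

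*Combined protocol and SAP*

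**What the plan says.** Section 11.1 assumes a 5.0% dislocation rate under standard templating and a 4.5-point difference, so an OPS rate below 0.5%. With alpha 0.05 and power 0.8 it obtains 414 participants. After 10% dropout, "this gives a total required sample size of 460, with 230 participants in each arm".

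The first 100 participants form an internal pilot, 50 per arm (Section 6). Of this pilot Section 11.1 says: "The internal pilot study will allow calculation of a provisional dislocation rate (the primary outcome) in the control arm of the study". The rule follows: "Using the dislocation rate in the internal pilot study and the minimum clinically significant difference of interest, we will re-calculate the sample size".

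Section 11.1 then presents as a consequence that "the full study sample size may change by 5% either way from our projected sample size of 476 participants". It foresees a possible return to the funder "if the size of the cohort increases by more than 5% (to above 500"). The Synopsis states the same expectation on a different base: "We anticipate the projected sample size of 460 may change by 5% either way". Section 6 also plans 230 per arm.

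On the likely control rate, Section 4 says: "Literature estimates indicate a true dislocation prevalence of 3 to 15" per cent.

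**The concern.** The rule subtracts a fixed 4.5 points from a proportion estimated in 50 patients. The planned control rate, 5.0%, is only half a point above the value at which the subtraction goes negative, and fiftieths move in steps of two points. The rule can therefore easily return nothing, and when it does return an N it can move a long way on one event. Section 4's own range also reaches below 4.5%.

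The recalculation is meant to secure the power of the full trial. If it yields no usable number and no fallback is written down, N will be chosen ad hoc after control-arm outcomes have been seen. The ±5% expectation tells the funder and the sites that any change will be small. The 476 base adds a plain inconsistency in the figure that triggers a return to the funder.

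**Working it through.** **Inputs.** Control rate 5.0%, difference 4.5 points, alpha 0.05, power 0.80, dropout 10% (Section 11.1); two-sided testing (Section 11.3); 1:1 allocation (Section 8.4); 50 pilot controls (Section 6).

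**1. The plan's own figure.** Pooled-variance formula, with p̄ = (p1 + p2)/2:

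n per arm = [1.96 √(2p̄(1−p̄)) + 0.8416 √(p1(1−p1) + p2(1−p2))]² / (p1 − p2)²

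With p1 = 0.05, p2 = 0.005 and p̄ = 0.0275: (0.4533 + 0.1928)² / 0.045² = 206.1, so 207 per arm and 414 in total. 414/0.9 = 460. Both stated figures reproduce exactly, so the same formula is a fair test of the rule.

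**2. The rule applied to 50 controls.** p1 = k/50, p2 = p1 − 0.045, total divided by 0.9.

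| Control events | Control rate | Implied OPS rate | Evaluable N | Total N | Versus 460 |
|---|---|---|---|---|---|
| 0 | 0% | −4.5% | none | none | – |
| 1 | 2% | −2.5% | none | none | – |
| 2 | 4% | −0.5% | none | none | – |
| 3 | 6% | 1.5% | 558 | 620 | +35% |
| 4 | 8% | 3.5% | 838 | 932 | +103% |
| 5 | 10% | 5.5% | 1108 | 1232 | +168% |

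**3. How often each happens.** Binomial with 50 controls:

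| True control rate | 0–2 events: no N | 3 events: 620 | 4 or more: 932 or above |
|---|---|---|---|
| 3% | 0.81 | 0.13 | 0.06 |
| 5% | 0.54 | 0.22 | 0.24 |
| 8% | 0.23 | 0.20 | 0.57 |

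At 5%, P(0–2) = 0.0769 + 0.2025 + 0.2611 = 0.5405. The 95% Clopper-Pearson interval for 2/50 is 0.5% to 13.7%, which shows how little 50 controls say about the rate.

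**4. Can the rule land within ±5%?** A total of 437 to 483 needs an observed control rate of about 4.87% to 5.15%. Fiftieths step from 4% to 6%, so no count gives it. With 45 evaluable controls (the stated 10% dropout), 0–2 events still give no N (probability 0.61 at 5%) and 3 events give 728. Over 45 to 55 evaluable controls the smallest defined total is 534 (3 of 55), above both 483 and 500.

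**5. Other formulas, 50 controls, 3/4/5 events.** Unpooled variance: 614/927/1225. Continuity-corrected: 716/1029/1327. Arcsine: 563/898/1207. None lies in 437–483 or 452–500. The one-sided uncorrected formula gives 489 at 3 events, but it gives 326 rather than 414 at the planned rates and conflicts with Section 11.3.

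**6. The anchor.** 460 × 0.95 = 437 and 460 × 1.05 = 483. 476 × 0.95 = 452 and 476 × 1.05 = 499.8, the source of the 500. 414/0.9 is 460, not 476. (414 × 1.15 = 476.1, so 476 may be left over from a 15% inflation; that is an assumption.)

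**7. Timing scenario.** If full 12-month pilot outcomes were required: 6 months of pilot recruitment + about 3 months' wait for surgery (Section 8.6) + 12 = month 21. At six recruits per week the remaining 360 take 360/6 = 60 weeks, or 13.8 months, so recruitment ends near month 20. If the 360 are instead spread evenly over the rest of a two-year period that includes the pilot, 100 + (15/18) × 360 = 400 of 460 are recruited by month 21.

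**8. Power of 460** (207 evaluable per arm) for a 4.5-point difference, normal approximation: 0.80 at a control rate of 5%, 0.67 at 6%, 0.50 at 8%, 0.40 at 10%, 0.28 at 15%.

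**The case against.** *The ±5% is an expectation, not a cap, and nothing enlarges the trial automatically.* This is true: increases go back to the funder, and substantial amendments need approval (Section 14.3). But that route covers increases only. At the planned rate the most likely outcome is no N at all, and no section deals with it.

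*The result depends on the number of evaluable controls.* It does. With 44 controls, 2 events give an N (386 with equal arms), and the chance of no N at 5% falls to about 0.35. With 39, 40 or 41 controls, 2 events give 480, 460 or 440; with 59 to 61, 3 events also fall within 437–483. These counts lie outside the stated 50 and its 10% dropout, and the in-band results are isolated: with 40 controls, one more event gives 856. Because the plan does not fix the follow-up at recalculation, the conclusion should be read as applying to 45 to 55 evaluable controls.

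*The effect could be held as a relative reduction instead.* The text uses 4.5 as an absolute difference and says nothing about rescaling it. Holding a 90% relative reduction gives 1169, 578, 380 or 283 for 1 to 4 events, again none within ±5%.

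*The month-21 problem is only a scenario.* Agreed. The rate is called provisional, so shorter follow-up may be intended. What is established is that the timing and follow-up are not stated.

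*The funder trigger may not be pure arithmetic.* The documents give a total grant but no per-patient budget, so they do not show which number is funded. That supports asking for 476 to be derived or replaced; it does not justify leaving two bases in the protocol.

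**Conclusion.** The concern holds and must be fixed. Followed as written with 50 controls, the rule gives no sample size with probability 0.54 at the planned 5% (0.81 at 3%, 0.23 at 8%). When it gives one, the smallest is 620. One event (2 versus 3) separates no answer from a trial 35% larger than planned; two events (2 versus 4) separate no answer from one about twice as large. The expected ±5% does not follow from the rule. This rests on a fixed absolute difference of 4.5 points, the two-sided formula that reproduces 414, and about 50 evaluable controls (45 to 55).

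The 476 base is a separate and smaller error, which moves the trigger for returning to the funder from 483 to 500. The unstated timing of the recalculation is a gap whose consequence depends on the follow-up intended.

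**What to change.** 1. In Section 11.1, replace 476 and 500 with 460 and 483, or show how 476 is derived and bring the Synopsis and Section 6 into line with it.
2. Delete, in Section 11.1 and the Synopsis, the statement that N is expected to change by only 5% either way.
3. Do not let the rule as written reset N. Choose one of:
   - (i) Keep 460 and use the pilot for feasibility only. State the power of 460 for a 4.5-point difference across control rates of 4.5% and above, and note that a 4.5-point reduction is impossible below that.
   - (ii) Keep re-estimation, with a stated time point and follow-up, a stated action when the observed control rate is below 4.5% (for example, N stays at 460), and a maximum N.

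**Cost.** Items 1 and 2 are wording only. Option (i) adds no patients. It gives up the check on the assumed 5%, which 50 controls inform only weakly, and accepts power of 0.50 if the control rate is 8% and 0.40 if it is 10%. Option (ii) keeps the check but may add patients and funding up to the maximum. It does not remove the sensitivity to single events (2 events would leave 460, 3 would ask for 620), so the maximum has to limit it.
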